## **5.11 Costs/Payments for participation**

There will be no costs to the subject for assessments, screening tests, and parking. The subject will be responsible for travel to/from the research site, unless it is not possible for them to do so. If subjects are unable to obtain transportation for research appointments, we will attempt to arrange a car service at no cost to the subject (e.g., taxi, medicab, Uber, Lyft). Subjects will be compensated with a total of \$60 for completing the study. Subjects in the usual care arm will be paid \$30 for the completion of each assessment; T1 and T2. Subjects in the intervention arm will be paid \$20 for the completion of each assessment; T1 and T2; and \$10 for each hepatotoxicity blood draw a week.

four and week 8 post-intervention. Payment will be in the form of pre-paid credit/debit card, gift card, or cash.

### **5.12 Return of research results**

All data collected as part of this study will be for research purposes only and subjects will be explicitly told that the experiment will not provide information as to their health status. Study personnel will inform the subject's clinical team if their scores on the cognitive test (MoCA) falls in the moderate range for cognitive impairment ( $\leq 19$ ).

---

## **6. SUBJECT WITHDRAWALS**

---

Subjects may discontinue participation in the study at any time if they decide they do not wish to take part any longer. Subjects may be withdrawn from the study by research personnel if it is deemed in their best interest to no longer participate or in the case of lack of cooperation, non-compliance, or other administrative reasons. If a subject withdraws from the study, the information they have already provided will be kept in a confidential manner.

---

## **7. REPORTABLE EVENTS**

---

An **adverse event (AE)** is any symptom, sign, illness, or experience that develops or worsens during the study, whether or not the event is considered related to the intervention. To assess the severity of adverse events, we will use the Common Terminology Criteria for Adverse Events (CTCAE) v5.0, recommended by the NCI. The CTCAE is available at <http://ctep.cancer.gov/reporting/ctc.html>. The CTCAE displays Grades 1 through 5 with unique clinical descriptions of severity for each adverse event based on this general guideline:

- Grade 1: Mild; asymptomatic or mild symptoms; clinical or diagnostic observations only; intervention not indicated.

- Grade 2: Moderate; minimal, local or noninvasive intervention indicated; limiting age-appropriate instrumental activities of daily living (ADL).
- Grade 3: Severe or medically significant but not immediately life-threatening; hospitalization or prolongation of hospitalization indicated; disabling; limiting self-care ADL.
- Grade 4: Life-threatening consequences; urgent intervention indicated.
- Grade 5: Death related to adverse event.

A serious adverse event (SAE) is any adverse medical experience that results in death, or is life-threatening, or requires inpatient hospitalization of at least 24 hours, or prolongs existing hospitalization, or results in persistent or significant disability/incapacity, or causes a congenital anomaly/birth defect, or requires medical or surgical intervention to prevent permanent impairment or damage.

**Stopping Criteria:** If disease progresses while on study and participant must restart cancer treatment, and participant is in the Intervention arm, participant will stop taking the study drug. Participant will still complete study measures. If disease progresses while on study and participant must restart cancer treatment, and participant is in the Usual Care arm, participant will still complete study measures. Any subject in the intervention arm with unexplained Grade  $\geq 2$  ALT, AST, or bilirubin increase will stop taking the study drug.

If a drug-related Grade  $\geq 3$  hepatotoxicity is observed in any subject in the intervention arm the study will be stopped. (See Section 11.3 for more information)

**Attribution:** An assessment of the relationship between the adverse event and study intervention, using the following categories.

ATTRIBUTION	DESCRIPTION
Unrelated	The AE is clearly NOT related to the intervention
Unlikely	The AE is doubtfully related to the intervention
Possible	The AE maybe related to the intervention
Probably	The AE is likely related to the intervention
Definite	The AE is clearly related to the intervention

The subject's referring oncologist, designee, or study medical monitor will determine the grade and attribution.

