**With that information, we will only report the following events:**

- Grade 3, 4, or 5 events that are possibly or probably related to the study intervention will be reported to the Data Safety Monitoring Committee and the Research Subjects Review Board (RSRB) at each continuing review.
- Serious, related, and unexpected events will be reported to the RSRB in an expedited manner.
- We will also maintain a record of these reportable events.

---

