### **11.3 Data and Safety Monitoring Plan**

The subject's physician will determine if the adverse event requires expedited review.

The James P. Wilmot Cancer Center Data Safety Monitoring Committee (DSMC) will serve as the DSMC of record for this study. The DSMC provides oversight of study progress and safety by review of accrual and events at regularly scheduled meetings. The frequency of review is determined by the size, risk and complexity of the trial, and has been assigned by the Cancer Center's Peer Review Committee at the time of their review and approval of each protocol.

The study PI will conduct continuous review of data and subject safety. The Investigator will submit (semiannual, annual) progress reports of these data to the DSMC for review. The review will include the number of subjects enrolled, withdrawals, significant toxicities as described in the protocol, and serious adverse events (both expected and unexpected). The Investigator will submit a copy of the AE spreadsheet along with the Progress Report to the DSMC for review. Actual review dates will be assigned when the first subject is accrued.

Any serious adverse event that is serious, related, and unexpected will be reported within 10 calendar days to both the Safety Coordinator and the RSRB. The DSMC Chair will determine whether further action is required, and when subject safety is of concern. When subject safety is of concern, an interim meeting may be called.

Serious adverse events that are related (either expected or unexpected) will be reported to the Committee for review at the quarterly meeting. SAE reports are expected to include enough detail so that the DSMC can determine the severity, toxicity grade, expectedness, treatment required, and a follow-up report documenting resolution of if there are sequelae. See *section 7. REPORTABLE EVENTS* for specific reporting requirements for this protocol.

---

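### No prompt report to the DSMC is tied to the liver stopping rule, so a Grade ≥3 liver event rated locally as not drug-related can wait for periodic review

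*Combined protocol and SAP*

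**What the plan says.** **The trigger.** Under Stopping Criteria in section 7, if a drug-related Grade ≥3 "hepatotoxicity is observed in any subject in the intervention arm the study will be stopped". The text then points to section 11.3. The same paragraph takes an individual EGCG subject off drug for an unexplained Grade ≥2 rise in ALT, AST or bilirubin.

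**Who decides.** Section 7 has five attribution categories, from Unrelated to Definite. The subject's "referring oncologist, designee, or study medical monitor will determine the grade and attribution". Section 5.6 states that the PI, subjects, personnel and statisticians are unblinded.

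**What is reported.** The list in section 7 opens with "With that information, we will only report the following events". Its first item is limited to Grades 3 to 5 and reads in part: "events that are possibly or probably related to the study intervention will be reported to the Data Safety Monitoring Committee". The RSRB receives the same report, in both cases at continuing review. Its second sends serious, related and unexpected events to the RSRB on an expedited basis.

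**Section 11.3.** An event that is "serious, related, and unexpected will be reported within 10 calendar days to both the Safety Coordinator and the RSRB". For the rest: "Serious adverse events that are related (either expected or unexpected) will be reported to the Committee for review at the quarterly meeting". The investigator also sends progress reports, with the interval written as semiannual, annual. These cover serious events and come with the AE spreadsheet. Two further routes are discretionary: the subject's "physician will determine if the adverse event requires expedited review", and "When subject safety is of concern, an interim meeting may be called".

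**The concern.** A single event of this kind ends the trial, so one would expect the plan to say how and when the independent committee learns of it. Section 7 refers to section 11.3. Section 11.3 describes general committee procedures, does not mention hepatotoxicity or the stopping rule, and refers back to section 7 for the reporting requirements. Neither place supplies the rule.

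What is at stake is the judgement on which the trigger depends. A Grade ≥3 liver event stops the study only if it is called drug-related, and that call is made locally with the treatment known. If it is rated Unlikely or Unrelated, the trial goes on, and nothing requires that anyone independent look at the rating promptly. A misattributed event would leave the other EGCG subjects on drug.

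**Working it through.** The plan gives no figure to reproduce here. The check traces each kind of Grade ≥3 liver event in the EGCG arm through sections 7 and 11.3.

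| Event as rated locally | Does the study stop? | Mandatory route to the DSMC |
|---|---|---|
| Related, serious, unexpected | Yes | Report to the Safety Coordinator and RSRB within 10 calendar days; the DSMC Chair decides on further action |
| Related, serious, expected | Yes | Quarterly meeting |
| Possible or Probable, not serious | Yes, if counted as drug-related | Continuing review (interval not stated), plus the progress report |
| Definite, not serious | Yes | Not on the section 7 list if read literally; AE spreadsheet with the progress report |
| Unlikely or Unrelated, serious | No | Progress report, which covers serious events without an attribution limit |
| Unlikely or Unrelated, not serious | No | AE spreadsheet with the progress report |

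Notes on the table:

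- Seriousness is defined separately from grade in section 7, so a Grade 3 ALT rise without admission can be non-serious.
- Section 8.1 names hepatotoxicity as a risk of EGCG without giving a grade, and expectedness is not defined. Either class is therefore open.
- Section 7 does not say which of the five categories count as drug-related.

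In the first four rows the study stops without any DSMC step, provided the event is counted as drug-related. A slow report there delays notice but does not by itself prolong dosing. The last two rows are where the study continues, and both rely on a periodic report.

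**Who remains exposed.** Allocation is 1:1, and a 12-week course lasts 12 / 4.345 = 2.76 months. Accrual is an assumption:

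- 40 subjects spread over the 18 months in section 2.4: 40 / 18 = 2.22 per month, half to EGCG = 1.11; 1.11 × 2.76 = 3.1 on drug at a time.
- The 4 per month in section 2.4, taken as enrolment: 2 per month to EGCG; 2 × 2.76 = 5.5.

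So about three to six EGCG subjects are on drug at once, counting the affected one.

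**Reporting load of a fixed rule.** There are 20 subjects in the arm (section 11.1). Expected reports = 20 × p, with p the assumed all-cause rate of Grade ≥3 liver events per subject, since the documents give none:

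- p = 1%: 20 × 0.01 = 0.2
- p = 2%: 20 × 0.02 = 0.4
- p = 5%: 20 × 0.05 = 1.0

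**The case against.** The best defence is that the plan already protects subjects where it counts.

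- A declared drug-related event stops the study with no committee step.
- An unexplained Grade ≥2 rise takes that subject off drug at a lower grade and needs no finding that the drug is to blame.
- EGCG subjects have liver tests at weeks 4 and 8 (section 5.9).
- Concerns raised at the weekly contact are reviewed with the treating oncologist and also the medical monitor, so there is a second look.
- The PI reviews safety data continuously, and progress reports cover serious events whatever their attribution.
- The DSMC's review frequency was assigned by the Cancer Center's Peer Review Committee, and the documents do not give the result.

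Most of this stands and limits the point to oversight. It does not close the gap. The medical monitor is one of the roles that may set the attribution. The individual stop depends on the rise being unexplained, which is again a local judgement, and it does nothing for other subjects. The expedited and interim routes are discretionary and not tied to this trigger. The missing Definite category is probably a wording slip, since such an event meets the stopping rule anyway.

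A reader might infer that subjects keep taking EGCG until the quarterly meeting after a drug-related event. The documents do not support that, because the stop does not wait for the meeting. A delay computed from the quarterly interval would therefore describe a case without continued dosing. It would also compare the date of a committee review with the date of a report.

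**Conclusion.** The concern holds as a minor gap in safety oversight. The trigger has no reporting rule attached, the cross-reference leads to no text on it, and a Grade ≥3 liver event rated Unlikely or Unrelated reaches the DSMC only periodically unless someone uses a discretionary route. The literal omission of Definite is a separate small defect.

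The size of the harm cannot be computed. It would need the rate of Grade ≥3 liver events and the share wrongly rated as not drug-related, and the documents give neither. A reader might take the chance of any such event among the 20 EGCG subjects as the chance that the gap matters. That would overstate it, because an all-cause rate includes events that would be called drug-related and would stop the study. The estimate of three to six subjects on drug rests on even accrual between the two assumed rates.

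**What to change.** In section 7 or 11.3, add: every Grade ≥3 ALT, AST or bilirubin event in the EGCG arm, whatever its attribution, seriousness or expectedness, is reported to the DSMC (through the Safety Coordinator) and to the RSRB within 10 calendar days. That is the interval the plan already uses. In the Grade 3 to 5 item of the section 7 list, change the attribution wording to *possibly, probably or definitely related*. The stopping trigger itself need not change.

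The cost is one sentence, one added word and a short report per event, including some for events judged unrelated. Visits, sample size and analysis are unaffected.

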**With that information, we will only report the following events:**

- Grade 3, 4, or 5 events that are possibly or probably related to the study intervention will be reported to the Data Safety Monitoring Committee and the Research Subjects Review Board (RSRB) at each continuing review.
- Serious, related, and unexpected events will be reported to the RSRB in an expedited manner.
- We will also maintain a record of these reportable events.

---

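### Section 7's Grade 3–5 reporting item leaves out 'Definite' attribution, so non-serious definite events (and, for the RSRB, serious but expected ones) have no stated event-level route

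*Combined protocol and SAP*

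**What the plan says.** Section 7 (Reportable Events) grades adverse events by CTCAE v5.0 and attributes them on five levels: Unrelated, Unlikely, Possible, Probably, Definite. The last is defined as "The AE is clearly related to the intervention".

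The reporting list opens with "With that information, we will only report the following events" and has three items:

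- "Grade 3, 4, or 5 events that are possibly or probably related to the study intervention" go to the DSMC and the RSRB at continuing review.
- "Serious, related, and unexpected events will be reported to the RSRB in an expedited manner".
- A record of these reportable events is kept.

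The stopping criteria in the same section say that if drug-related Grade 3 or higher "hepatotoxicity is observed in any subject in the intervention arm the study will be stopped. (See Section 11.3 for more information").

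Section 11.3 (Data and Safety Monitoring Plan) adds three routes:

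- Events that are "serious, related, and unexpected will be reported within 10 calendar days to both the Safety Coordinator and the RSRB".
- "Serious adverse events that are related (either expected or unexpected) will be reported to the Committee for review at the quarterly meeting".
- A progress report to the DSMC, with its interval left as semiannual or annual, that covers significant toxicities and serious events and is accompanied by the AE spreadsheet.

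For the protocol's specific reporting requirements, Section 11.3 refers back to Section 7.

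**The concern.** The list is exclusive, and its Grade 3–5 item stops one level short of the top of the protocol's own scale. Within that item, an event drops out of reporting when its attribution rises from probable to definite, which is the reverse of what a safety rule should do. Section 5.9 also routes safety concerns from the weekly contacts through Section 7, so staff will work from this list.

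At stake is whether the RSRB is told of a limited but relevant set of events. Section 8.1 names hepatotoxicity as a risk, and Section 5.9 schedules liver tests at weeks four and eight in the intervention arm. A Grade 3 liver event found on such a test, judged definitely related and managed without hospital admission, is a plausible event in this trial and lies outside the list. It is also an event that stops the study, and the cross-reference that should explain what happens next leads to no text on the matter.

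**Working it through.** No arithmetic on trial figures applies. The check takes every Grade 3–5 event rated 'Definite', splits it by seriousness and expectedness, and runs each combination through every reporting route in Sections 7 and 11.3. The two sections are read cumulatively, which is the reading most favourable to the plan.

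| Definite, Grade 3–5 | Section 7, Grade 3–5 item | Section 7, expedited item | Section 11.3, event-level | RSRB route | DSMC route |
|---|---|---|---|---|---|
| Serious, unexpected | No | Yes | Yes (10 days; quarterly meeting) | Yes | Yes |
| Serious, expected | No | No | Yes (quarterly meeting) | None stated | Yes |
| Non-serious, unexpected | No | No | No | None stated | Progress report and AE spreadsheet only |
| Non-serious, expected | No | No | No | None stated | Progress report and AE spreadsheet only |

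Counts for 'Definite':

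- Outside the Grade 3–5 item: 4 of 4 combinations.
- Outside the whole Section 7 list: 4 − 1 = 3 of 4, because the expedited item covers the serious, unexpected events.
- No event-level route in either section: 3 − 1 = 2 of 4, because Section 11.3 covers the serious, expected events for the DSMC.
- No stated RSRB route: 3 of 4.

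The same exercise for 'Probably' leaves 0 of 4 combinations outside the list, since the Grade 3–5 item takes all of them to both bodies. The whole difference comes from the missing category.

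Which grades fall in the gap: death and life-threatening events meet Section 7's definition of a serious adverse event, so Grade 5 events and life-threatening Grade 4 events are serious. The two non-serious rows are therefore mainly Grade 3. Section 7's general description of Grade 3 includes events that are medically important without an immediate threat to life, so a laboratory-detected liver abnormality can be Grade 3 without being serious.

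Cross-reference: Section 7's stopping rule points to Section 11.3. That section mentions neither hepatotoxicity nor the stopping rule, and refers the reader back to Section 7. Neither section says who is told, or when, once the stopping event occurs. Adding the missing category would not settle this: a non-serious stopping event rated possible or probable is already in the list, but its only stated timing is continuing review.

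**The case against.** The strongest reply is that this is a drafting slip with little practical effect. Elsewhere in Section 7's list and in Section 11.3, 'related' is used without an upper limit, so nothing suggests that the authors meant to exclude definite events. The Grade 3–5 item is routine, not expedited, reporting, so even a probable event waits for periodic review. Other safeguards do not depend on attribution. Section 5.9 has concerns from weekly contact graded, recorded and reviewed with the treating oncologist and the medical monitor. Section 11.1 reports the total and severity of AEs by group. Section 11.3 provides continuous review by the investigator, a progress report covering significant toxicities, and the possibility of an interim DSMC meeting.

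Most of this stands, and it limits the point. It rules out three stronger readings that a reader might infer:

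- That definitely related events as a class go unreported. They do not: those that are serious and unexpected are expedited, and all related serious events reach the DSMC.
- That the stopping rule is disabled. It is triggered by drug-related hepatotoxicity of Grade 3 or above being observed. It does not depend on the reporting list and has no attribution ceiling, so it still operates.
- That hepatotoxicity necessarily misses expedited reporting because Section 8.1 lists it as a risk. That needs hepatotoxicity to be classed as expected, and the documents do not define expectedness.

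What the reply does not answer is the literal text. An exclusive list that names two of the three related levels requires staff to assume that 'probably' includes 'Definite', although the protocol's own table separates them. No other passage gives the RSRB a route for the events in the gap.

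**Conclusion.** The item is wrong as written, within a narrow scope. Two groups of definitely related events are affected. Non-serious events of Grade 3 or above, mainly Grade 3, have no stated RSRB route and reach the DSMC only in the periodic progress report and AE spreadsheet. Serious but expected events reach the DSMC at its quarterly meeting but have no stated RSRB route. Recording of AEs, the planned AE summaries and the operation of the stopping rule are not affected.

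The conclusion assumes that the list is followed literally and that Sections 7 and 11.3 apply together. If Section 7's exclusive wording were taken to override Section 11.3, the gap would be wider. How many events fall in the serious but expected group depends on how expectedness is judged. The cross-reference that leads nowhere is a separate defect and holds whatever is decided about the missing category.

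**What to change.** In Section 7, change the Grade 3–5 item to read *possibly, probably or definitely related*. This closes both parts of the gap, because the item applies whether or not an event is serious or expected and goes to both bodies.

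Then reconcile the stopping rule's cross-reference with Section 11.3. Either add a sentence there stating how the event that triggers the rule is reported, to whom and by when, or point the reference to wherever that is stated. The stopping rule itself need not change for this purpose.

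The cost is one added word (with the joining word moved) in Section 7 and about one sentence in Section 11.3. It needs no additional data, assessments or analysis.

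### Section 7 leaves the Definite attribution level out of its Grade 3-5 reporting rule; other routes cover part of the gap, but non-serious Definite events and, for the RSRB, expected Definite SAEs are left without an event-reporting rule

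*Combined protocol and SAP*

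**What the plan says.** The attribution table in Section 7 has five levels: Unrelated, Unlikely, Possible, Probably and Definite. The last two are separate rows. One reads "Probably The AE is likely related to the intervention". The description for Definite is "The AE is clearly related to the intervention".

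The reporting list that follows opens with "With that information, we will only report the following events". Its first item is "Grade 3, 4, or 5 events that are possibly or probably related to the study intervention will be reported to the Data Safety Monitoring Committee". That sentence also names the RSRB, at each continuing review. Its second item is "Serious, related, and unexpected events will be reported to the RSRB in an expedited manner". A third item promises a record of these reportable events.

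Section 11.3 sets out further reports on different criteria. "Any serious adverse event that is serious, related, and unexpected will be reported within 10 calendar days to both the Safety Coordinator and the RSRB". For the DSMC, it says: "Serious adverse events that are related (either expected or unexpected) will be reported to the Committee for review at the quarterly meeting". The investigator also sends the DSMC progress reports, at an interval left as semiannual or annual. They cover significant toxicities and all SAEs, expected or not, and a copy of the AE spreadsheet goes with them. The section ends by pointing back to Section 7 for the protocol's specific reporting requirements.

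Separately, the stopping criteria in Section 7 stop the study if a drug-related hepatotoxicity of Grade 3 or higher occurs in the intervention arm.

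**The concern.** A rule that reports an event when the assessor thinks it possibly or probably caused by the intervention should also report it when the assessor is sure. As written it does not. Moving an event up one level, from Probably to Definite, takes it out of the Section 7 Grade 3-5 rule. The exclusive opening means that the list cannot be read as a set of examples, and nothing in the protocol says that Probably includes Definite. This is very likely a drafting slip, but staff apply the text as it stands.

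At stake is whether the two oversight bodies receive, on a defined schedule, the severe events with the strongest causal attribution. Safety is part of Aim 1 (Section 2.3), and Section 8.1 names hepatotoxicity as a risk of the supplement. Sections 7 and 11.3 also leave the word related unmapped to the five levels, so staff must decide for themselves which events each sentence covers.

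**Working it through.** The plan gives no figure to reproduce, and no sample-size or power formula applies. The check is a literal reading of each event-reporting rule for Grade 3-5 events.

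**Inputs**
- Levels counted as related: Possible, Probably, Definite. This is an assumption, because neither section defines the term.
- Route A (Section 7, first item): level is Possible or Probably; goes to the DSMC and the RSRB.
- Route B (Section 7, second item, and Section 11.3): serious, related and unexpected; goes to the RSRB.
- Route C (Section 11.3): serious and related; goes to the DSMC quarterly.

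**Rules.** The RSRB is reached if A or B applies. The DSMC is reached if A or C applies. The progress report and spreadsheet are set aside here and added back below, because they are periodic submissions and not event-reporting rules.

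**Classes.** 3 levels x 2 (serious or not) x 2 (expected or not) = 12.

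| Class | A | B | C | RSRB | DSMC |
|---|---|---|---|---|---|
| Possible or Probably, serious, unexpected (2 classes) | yes | yes | yes | yes | yes |
| Possible or Probably, serious, expected (2 classes) | yes | no | yes | yes | yes |
| Possible or Probably, non-serious, expected or unexpected (4 classes) | yes | no | no | yes | yes |
| Definite, serious, unexpected | no | yes | yes | yes | yes |
| Definite, serious, expected | no | no | yes | no | yes |
| Definite, non-serious, unexpected | no | no | no | no | no |
| Definite, non-serious, expected | no | no | no | no | no |

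**Counts.** Both bodies are reached in 8 + 1 = 9 of 12 classes. Within Definite, 3 of 4 classes have no RSRB rule and 2 of 4 have no DSMC event rule. If Route A also named Definite, all 12 classes would reach both bodies. These are counts of classes, not probabilities: the classes are not equally likely, and the plan gives no event rates.

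**Adding the periodic route.** The spreadsheet has no stated filter on grade, seriousness or attribution, so the DSMC should see non-serious Definite events there, at the progress-report interval. Section 11.3 sends the progress report and spreadsheet to the DSMC and does not mention the RSRB as a recipient.

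**What the non-serious classes contain.** Section 7 describes Grade 4 as life-threatening and Grade 5 as death, and its SAE definition includes both. The non-serious Definite classes therefore consist mainly of Grade 3 events that meet no SAE criterion.

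**The case against.** The strongest reply is that the omission has little practical reach. Definite SAEs still go to the DSMC each quarter, and unexpected ones go to the RSRB within 10 calendar days. The DSMC receives the AE spreadsheet. Weekly safety concerns are graded, recorded and reviewed with the treating oncologist and the medical monitor (Section 5.9). Sections 7 and 11.3 differ partly because they address different recipients and schedules, so a difference between them is not in itself a contradiction. All of this stands, and it limits the point.

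A reader might infer that the most clearly drug-caused severe events escape reporting altogether. The documents do not support that. The omission is from one item in the Section 7 list, and the routes above pick up every Definite SAE for the DSMC and the serious, unexpected ones for the RSRB.

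A reader might also take a Grade 3 liver-test rise as the typical missed event. The stopping criteria answer most of that: an event judged clearly related is drug-related on any ordinary reading, so a Definite hepatotoxicity of Grade 3 or higher would stop the study and could hardly go unnoticed. It remains true that the stopping text does not say which oversight body is told. It refers to Section 11.3, which mentions neither hepatotoxicity nor stopping. Definite Grade 3 events of other kinds have no such backstop.

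Finally, a reader might suppose that the Aim 1 safety results would be distorted. They would not be. Section 11.1 reports total AEs and their severity per group, whatever the attribution or reporting status.

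These replies do not cover two things: an RSRB rule for non-serious Definite events and for expected Definite SAEs, and an event-reporting rule to the DSMC for the non-serious ones.

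**Conclusion.** The point holds in a narrow form. On a literal reading, the Section 7 Grade 3-5 rule omits the strongest attribution level. After every other stated route is counted, two gaps remain:

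- Non-serious Definite events of Grade 3 or higher have no event-reporting rule to the RSRB, and reach the DSMC only through the periodic progress report and spreadsheet.
- Expected Definite SAEs have no RSRB rule.

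This is 3 of the 12 classes of related event for the RSRB and 2 of 12 for a DSMC event rule. The count assumes that related means Possible, Probably or Definite, and that the Section 11.3 reports apply despite the exclusive wording in Section 7.

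How many events would be affected cannot be worked out from the documents, which give no rate for Definite, non-serious Grade 3 events. A claim about how much of the safety signal would be lost has no basis in them. No sample size or efficacy result changes. It is a wording defect in safety oversight, worth correcting because the rule as written runs against its evident purpose.

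**What to change.** Three wording changes, which one short amendment can carry:

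1. In the first item of the Section 7 list, change the attribution wording to *possibly, probably or definitely related*.
2. State once that *related*, in the reporting rules of Sections 7 and 11.3, means those three levels. The sponsor should also say whether the same meaning applies to the term drug-related in the stopping criteria.
3. Reconcile the word *only* in Section 7 with the additional reports in Section 11.3. Either delete it, or add to the Section 7 list the quarterly DSMC report of related SAEs and the progress report that covers all SAEs.

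The first change closes the gap: all 12 classes then reach both bodies. The other two remove the ambiguity about which section governs. The cost is a brief protocol amendment. No new data collection, visits or analyses are needed, because grade and attribution are already assigned under Section 7.
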